5.1. Summary of Study Design

Study I8B-MC-ITSI is a Phase 3, prospective, randomized, double-blind, outpatient, multinational, multicenter, 2-treatment group, crossover, active-controlled study conducted in patients with type 1 diabetes (T1DM) currently using CSII. In the 2 treatment groups, LY900014 and insulin lispro, meal bolus doses will be delivered immediately prior to each meal (0 to 2 minutes) in a double-blind manner.

The study includes a 1-week screening period and a 2-week lead-in period followed by a 2-period (Period I and Period II) crossover and a 4-week post-treatment safety follow-up. Each period of the crossover will consist of 6 weeks of treatment with no washout between periods.

Figure ITSI.5.1 illustrates the study design.

[figure not shown]

Figure ITSI.5.1. Illustration of study design for Clinical Protocol I8B-MC-ITSI.

Patients who need to discontinue from study treatment will also be discontinued from the study. Please refer to Protocol Sections 8.1 and 8.2. In this document, discontinuation of IP refers to the last dose of IP in a study period (lead-in, Period I, or Period II).

The eCOA diary will be used by patients to document 4-point SMBGs (consists of fasting [pre-morning meal], pre-midday meal, pre-evening meal, and pre-bedtime), hypoglycemia, and all infusion set changes, including date and time of change, designation of routine or premature change, primary reason for premature change (infusion set kinked, came out, or leaking; empty

pump reservoir; infusion site pain or redness; pump occlusion alarm; suspected infusion set occlusion; other) as depicted in Protocol 9.1.4.1. Additional data on infusion site complications will be collected by investigators.

Patients will enter all non-meal-related correction boluses into the eCOA diary. In the case of suspected infusion set occlusion, patients will choose or enter a new correction bolus from the eCOA diary that corresponds to the time of the suspected occlusion. They will then indicate if the correction bolus was given via pump or via syringe. If more than one correction bolus is given, patients should choose the first non-meal related correction bolus. This information is also critical in order to evaluate the primary objective of the study.

Pump interruption is defined as patient is off pump due to pump malfunction and is temporarily using injection therapy. It does not include the condition where patient uses a syringe to inject a correction bolus dose while still on pump. Any interruption of CSII will need to be documented in the electronic case report form (eCRF). When patients resume use of pump following the interruption, the infusion set insertion should be entered as “routine” infusion set change in eCOA.

[figure not shown]

Figure ITSI.5.2. Flow chart for reporting infusion set changes.

5.2. Determination of Sample Size

Approximately 48 patients (24 patients in each treatment sequence) will be randomized in order that approximately 42 patients complete the study.

The primary objective of this study is to compare LY900014 and insulin lispro with respect to the rate (events/patient/30 days) of infusion set failures that lead to premature infusion set changes, due to a pump occlusion alarm OR due to unexplained hyperglycemia with blood

glucose (SMBG) >250 mg/dL (13.9 mmol/L) that does not decrease within 1 hour following a correction bolus delivered via the pump, during the 6-week treatment period.

The study was designed following a regulatory interaction to assess the safety comparability of LY900014 and insulin lispro. It is not designed or powered to be a non-inferiority or superiority trial.

Assuming a 12% dropout rate after randomization, approximately 48 patients (24 patients in each treatment sequence) will need to be randomized.

5.3. Method of Assignment to Treatment

Patients who meet all criteria for enrollment and complete the lead-in period will be randomized to double-blind treatment at Visit 3. Assignment to treatment sequences will be determined by a computer-generated random sequence using an interactive web-response system (IWRS).

Patients will be randomized to 1 of the 2 treatment sequences in a 1:1 ratio:

Sequence A: LY900014 → insulin lispro

Sequence B: insulin lispro → LY900014

Stratification will be by region (US, OUS), historical use of SmartGuard/Threshold Suspend (Yes, No), and HbA1c stratum ($\leq 7.3\%$, $> 7.3\%$ at Visit 1).

6. A Priori Statistical Methods

6.1. General Considerations

Statistical analysis of this study will be the responsibility of Eli Lilly and Company (hereafter Lilly). Any change to the data analysis methods described in the protocol will require an amendment ONLY if it changes a principal feature of the protocol. Any other change to the data analysis methods described in the protocol, and the justification for making the change, will be described in this SAP and/or in the clinical study report (CSR). Additional exploratory analyses will be conducted, as deemed appropriate.

For purposes of analysis, the following populations are defined in [Table ITSI.6.1](#):

Table ITSI.6.1. Patient Populations

Population	Description
Entered	All patients who give informed consent.
Enrolled	All patients who receive at least 1 dose of open-label insulin lispro in the 2-week lead-in period.
Randomized	All patients who are randomly assigned to study treatment at Visit 3. Treatment group will be defined on the basis of the treatment the patients are assigned to.
Safety	All randomized patients who receive at least 1 dose of the randomly assigned IP. Treatment group will be defined on the basis of the treatment the patients are assigned to.
CGM Population	All randomized patients who receive at least 1 dose of the randomly assigned IP, and have CGM data from at least 1 collection period (lead-in, Period I and Period II). Treatment group will be defined on the basis of the treatment the patients are assigned to.

Safety analyses will be conducted on the Safety Population. Analyses of adverse events (AEs) will include all data collected during the course of the entire 6-week treatment period for each treatment group regardless of IP use. Analyses of hypoglycemia will be conducted on data collected prior to permanent discontinuation (i.e., last dose) of IP in each 6-week treatment period. Unless otherwise specified, pump-related safety analyses (e.g., infusion set failures, interstitial glucose reduction rate) will exclude data (if any) that are collected while patients temporarily are off pump or off IP. Data collected during the safety follow-up period will not be used for comparisons between treatment groups.

Unless otherwise specified, exploratory efficacy analyses will be conducted on the Randomized Population. CGM outcome analyses will be conducted on the CGM Population.

Unless otherwise noted, all tests of treatment effects will be conducted at a 2-sided alpha level of 0.05, and confidence intervals (CIs) will be calculated at 95%, 2-sided. If conducted, all tests of interactions between treatment groups and other factors will be conducted at a 2-sided alpha level of 0.10.

The definitions of baseline and post-baseline for the safety and efficacy analyses depend on which analysis period is being used. The following analysis periods will be used:

- Lead-in Period – Visits 2-3
- 12-Week Treatment Period while on IP – from first dose to last dose of IP in each 6-week randomized treatment period (Period I and Period II)
- 12-Week Treatment Period Regardless of IP use – from randomization to Week 6 of each randomized treatment period (including all data regardless of IP use)
- Safety Follow-up Period – Visit 801

Table ITSI.6.2 describes the rules for determining the patient population, baseline and postbaseline observations for the different analysis periods. The data in the lead-in and the safety follow-up visit, if summarized, will be for overall, not by treatment group.

The data on IP is defined based on the following rules:

- for data only measured at an office visit (for example, HbA1c), if the office visit date (or laboratory sample collection date) is within 14 days of the date of last study drug dose of the randomized treatment period (Period I or Period II), then postbaseline data measured at or prior to that office visit will be considered as data on IP.
- for data collected as running records with an exact date and/or time stamp such as diary entries where the date and time of the measures was not tied with the date of an office visit, postbaseline data with date and time \leq (last study drug dose date and time) will be considered as data on IP.

For continuous measures, summary statistics will include sample size, mean, standard deviation (SD), median, minimum, and maximum for both the actual and the change from baseline measurements. Least squares (LS) means and standard errors derived from the analysis models will also be displayed for the change from baseline measurements. Treatment comparisons will be displayed showing the treatment difference LS means and the 95% CIs for the treatment differences, along with the p-values for the treatment comparisons.

Unless otherwise specified, a restricted maximum likelihood based, mixed-effect model repeated measures (MMRM) analysis will be used to analyze continuous longitudinal variables. All the longitudinal observations at each scheduled postbaseline visit during the 6-week treatment period for each treatment group will be included in the analysis. An unstructured covariance structure will be used to model the within-patient errors. Significance tests will be based on LS means and Type III tests. SAS PROC MIXED will be used to perform the analysis.

- MMRM-Model 1: for analysis of variables that are measured at multiple designated visits within each randomized treatment period (e.g., weight and vital signs), the model will include the fixed class effects of treatment, period, sequence, strata (region, historical use of SmartGuard/Threshold Suspend, HbA1c), week (relative to the start of each randomized treatment period), and week-by-treatment interaction, and the continuous, fixed covariate of baseline value. If the analysis fails to converge, the following covariance structures will be tested in order:

- Compound symmetry with heterogeneous variances
- Compound symmetry without heterogeneous variances
- MMRM-Model 2: for analysis of variables that are only measured once for each randomized treatment period (e.g., 1,5 AG), the model will include the fixed class effects of treatment, period, sequence, strata (region, historical use of SmartGuard/Threshold Suspend, HbA1c), and the continuous, fixed covariate of baseline value (Grizzle 1965). If this analysis fails to converge, a covariance structure of compound symmetry without heterogeneous variances will be used.

The Kenward-Roger approximation will be used to estimate denominator degrees of freedom. For either of the two models, if the model fails to converge for any covariance structure, strata may be deleted from the model.

For categorical measures (such as incidence of AEs), summary statistics will include sample size, frequency, and percentages. Prescott's test will be used for treatment comparisons, unless otherwise specified.

For laboratory values, both conventional (CN) and Systeme International (SI) units will be presented. Therefore, both % and mmol/mol will be presented for HbA1c and both mg/dL and mmol/L will be presented for glucose measurements.

Table ITSI.6.2. Baseline and Post-Baseline Definitions and Patient Population by Study Period and Type of Analysis

Study Period/Analysis	Patient Population	Baseline Observations	Post-Baseline Observations
Lead-In Period (Overall¹ only)			
TEAEs	All Enrolled Patients	Prior to first dose of open-label insulin lispro (or Visit 2 date if the dose date is missing)	The entire lead-in period after first dose of open-label insulin lispro and prior to first dose of IP (or Visit 3 date if the dose date is missing)
Basal, bolus, and total insulin doses, and bolus/total insulin dose ratios continuous analysis	All Randomized Patients	Visit 2	Visit 3 prior to first dose of IP
Weight and vital signs	All Randomized Patients	Last of Visits 1-2	Visit 3
Pump factors - breakfast CR, AIT, breakfast ISF)	All Randomized Patients	Visits 2	Visit 3 prior to first dose of IP, excluding data (if any) that are collected while patients temporarily are off pump or off open-label insulin lispro
Pump factor - frequency of use of non-normal bolus type [Square Wave or Dual Wave] ³	Population with a baseline and at least one post-baseline observation	Visit 2	Visit 3

Study Period/Analysis	Patient Population	Baseline Observations	Post-Baseline Observations
12-Week Treatment Period While on IP (from first to last dose of IP in each 6-week randomized treatment period)			
Infusion set failures	All Patients in the Safety Population	From first to last dose of open-label insulin lispro, excluding data (if any) that are collected while patients temporarily are off pump or off open-label insulin lispro	From first to last dose of IP in each randomized treatment period (Period I and Period II), excluding data (if any) that are collected while patients temporarily are off pump or off IP
Premature infusion set changes by reason (infusion set kinked, came out or leaking; empty pump reservoir; infusion site pain or redness; pump occlusion alarm; suspected infusion set occlusion; other)	All Patients in the Safety Population	From first to last dose of open-label insulin lispro, excluding data (if any) that are collected while patients temporarily are off pump or off open-label insulin lispro	From first to last dose of IP in each randomized treatment period (Period I and Period II), excluding data (if any) that are collected while patients temporarily are off pump or off IP
Time interval until infusion set change	All Patients in the Safety Population with a baseline and a post-baseline observation	From first to last dose of open-label insulin lispro, excluding data (if any) that are collected while patients temporarily are off pump or off open-label insulin lispro	From first to last dose of IP in each randomized treatment period (Period I and Period II), excluding data (if any) that are collected while patients temporarily are off pump or off IP
Basal, bolus, and total insulin doses, bolus/total insulin dose ratios	All Patients in the Randomized Population with a baseline and a post-baseline observation	Visit 3 prior to first dose of IP	Visits 4, 6, 7, and 9 prior to last dose of IP in each randomized treatment period (Period I and Period II)
CGM outcome variables (including interstitial glucose reduction rate)	All Patients in the CGM Population (with a baseline and a post-baseline observation for continuous variables, unless otherwise ²)	From first to last dose of open-label insulin lispro, excluding data (if any) that are collected while patients temporarily are off pump or off open-label insulin lispro	From first to last dose of IP in each randomized treatment period (Period I and Period II), excluding data (if any) that are collected while patients temporarily are off pump or off IP
Hypoglycemia events	All Patients in the Safety Population	From first to last dose of open-label insulin lispro	Visits 4, 5, 6, 7, 8 and 9 after first dose of IP and prior to last dose of IP in each randomized treatment period (Period I and Period II)
HbA1c summary statistics	All Randomized Patients with a baseline and at least one post-baseline observation while on IP	Last of Visit 1-3 prior to the first dose of IP	Visits 6 and 9

Study Period/Analysis	Patient Population	Baseline Observations	Post-Baseline Observations
1,5 AG	All Randomized Patients with a baseline and at least one post-baseline observation while on IP	Last of Visit 1-3 prior to the first dose of IP	Visits 6 and 9
Pump factors - breakfast CR, AIT, breakfast ISF)	All Patients in the Safety Population with a baseline and at least one post-baseline observation	Visit 3 prior to the first dose of IP excluding data (if any) that are collected while patients temporarily are off pump or off open-label insulin lispro	Visits 4, 6, 7, and 9 prior to last dose in IP of each randomized treatment period (Period I and Period II) excluding data (if any) that are collected while patients temporarily are off pump or off IP
Pump factor - frequency of use of non-normal bolus type [Square Wave or Dual Wave] ³	Population with a baseline and at least one post-baseline observation	Visit 3	Visit 4, 6, 7, 9
12-Week Treatment Period Regardless of IP use (from randomization to Week 6 of each randomized treatment period regardless of IP use)			
TEAEs	All Patients in the Safety Population	Prior to first dose of randomized IP (or Visit 3 if the dose date is missing) but after the first dose of open-label insulin lispro in the lead-in period	From randomization to Week 6 of each randomized treatment period regardless of IP use
Weight and vital signs	All Patients in the Safety Population with a baseline and a post-baseline observation	Last of Visits 2-3	Visits 4, 6, 7, and 9 regardless of IP use
Safety Follow-Up Visit (Overall¹ Only)			
TEAEs	All Patients in the Safety Population who enter the safety follow-up period	After first dose of IP and prior to last dose of IP in the 12-Week Treatment Period	From the date of the last visit of the 12-Week treatment period to the end of study
Weight and vital signs	All Patients in the Safety Population who enter the safety follow-up period	Last of Visits 2-3	Visits 801

Abbreviations: 1,5-AG = 1,5-Anhydroglucitol; CGM = Continuously Glucose Monitoring; CR = carb ratio; HbA1c = hemoglobin A1c; IP = investigational product; MMRM = mixed-effect model repeated measures; SMBG = self-monitored blood glucose; TEAE = treatment-emergent adverse event

Note:

- ¹ Overall means that data will be summarized in total and no by-treatment group summary or statistical analysis will be included.
- ² Not required for the interstitial glucose reduction rate and duration of each individual hypoglycemic episode because it is possible that some patients may not have any non-meal related correction bolus or hypoglycemic event to baseline values.
- ³ Per protocol, pump factor - frequency of use of non-normal bolus type [Square Wave or Dual Wave] were collected over the 7 days prior to designated visits, when patients were on pump and on IP.

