### **7.1.3. Method of Treatment Assignment**

Patients who meet all criteria for enrollment and complete the lead-in period will be randomized to double-blind treatment at Visit 3. Assignment to treatment sequences will be determined by a computer-generated random sequence using an interactive web-response system (IWRS).

Patients will be randomized to 1 of the 2 treatment sequences in a 1:1 ratio:

Sequence A: LY900014 → insulin lispro

Sequence B: insulin lispro → LY900014

Stratification will be by region (US, OUS), historical use of SmartGuard/Threshold Suspend (Yes, No), and HbA1c stratum ( $\leq 7.3\%$ ,  $> 7.3\%$  at Visit 1).

Patients will fill a new pump reservoir and infusion set with IP, then insert a new pump infusion set cannula into an appropriate site, and begin infusion of IP prior to leaving the investigative site at Visits 2, 3, and 6. Patients will continue to fill reservoirs and infusion sets with IP and insert a new infusion set cannula into an appropriate site every  $72 \pm 4$  hours as outpatients, unless a change is required for failure of the infusion set.

The IWRS will be used to assign all IP during the study, including insulin lispro during the lead-in period. The IWRS will be used to assign vials containing double-blind IP to each patient randomized to the sequence of treatment groups. Site personnel will confirm that they have located the correct vials by entering a confirmation number found on the vials into the IWRS.

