6.9. Important Protocol Deviations

Important protocol deviations that potentially compromise data integrity or patients' safety will be summarized by treatment group for all randomized patients. [Table ITSI.6.3](#) lists the categories/subcategories of important protocol deviations, source of identification, and the method to identify each deviation.

Table ITSI.6.3. Description of Important Protocol Deviations

Category	Sub-categories	Trial Specific	Source	Methods of Identification
Informed Consent	Informed Consent Not Obtained	N/A	Mixed (monitoring and clinical database)	Compare all assessment dates to ICD date (except those assessments that may occur before ICD, e.g., disease assessments).
Informed Consent	Improper Consent	N/A	Mixed (monitoring and clinical database)	Failure to re-consent after an ICD amendment at first possible visit. Unauthorized personnel administered ICD. Patient signed incorrect version of ICD. ICD was not dated. ICD was lost.
Informed Consent	Revoke Consent	N/A	Mixed (Monitoring and clinical database)	Patient revoked ICD. If patient revokes consent, data are excluded from the study.
Eligibility	Inclusion/Exclusion	Type of Patient and Disease Characteristics	Mixed (monitoring and clinical database)	CRF (Medical History: Diabetes Duration panel) data indicate diagnosis date of T1D <1 year prior to screening date (#1). CRF (Prior Diabetes Therapies/Concomitant panel) data to indicate start date for continuously using insulin < 1 year prior to screening date (#1). Also identified by CRA as captured in sCTMS.

Category	Sub-categories	Trial Specific	Source	Methods of Identification
Eligibility	Inclusion/Exclusion	Age not in compliance with entry criteria	Mixed (monitoring and clinical database)	CRF data indicate the age <18 yrs at Visit 1 (#2). Also identified by CRA as captured in sCTMS.
Eligibility	Inclusion/Exclusion	Previous non-insulin antihyperglycemic medications	Mixed (monitoring and clinical database)	CRF Prior Diabetes Therapies / Concomitant Therapy panel data to indicate not compliant with entry criteria #42. Also identified by CRA as captured in sCTMS.
Eligibility	Inclusion/Exclusion	Previous insulin therapy	Mixed (monitoring and clinical database)	CRF Prior Diabetes Therapies / Concomitant Therapy panel data to indicate not compliant with entry criteria #5 [basal insulin was used for >14 consecutive days during the 6 months prior to screening], #6, or #41 Also identified by CRA as captured in sCTMS.

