Eligibility	Inclusion/Exclusion	Other Inadvertent Enrollment	Non Programmable (monitoring)	Identified by CRA as captured in sCTMS.
Eligibility	Inclusion/Exclusion	Use of non-study device or materials	Non Programmable (monitoring)	Use of non-study pumps, infusion sets, and use of Enlite sensor (enables Smart-Guard)
Investigational Product	Treatment Assignment/ Randomization Error	N/A	Non Programmable (monitoring)	IWRS data entry errors that impact patient stratification, for example, lab data indicated different strata from IWRS stratification report. Dispensing error: Patient is assigned to a treatment, but site gave a different treatment to the patient.
Investigational Product	Unblinding	N/A	Non Programmable (monitoring)	Any inadvertent unblinding affecting, patients, investigator or sponsor.
Investigational Product	Patient Took Medication Not Fit for Use	N/A	Non Programmable (monitoring)	Study Drug not fit for use administered to patient.

Category	Sub-categories	Trial Specific	Source	Methods of Identification
Investigational Product	Other	Use of expired CT material	Non Programmable (monitoring)	Also identified by CRA as captured in sCTMS.
Study Procedures	Other	Infusion set change frequency	Programmable (clinical database)	eCOA data indicate that $\geq 75\%$ of routine infusion set changes are not in the range of 72 ± 4 hours during the two 6-week treatment periods (#13).
Study Procedures	Violation of Discontinuation Criteria	N/A	Mixed (monitoring and clinical database)	Patients not discontinued from study despite having met protocol specified discontinuation criteria. Also identified by CRA as captured in sCTMS. Protocol Section 8 (e.g., patient(s) become pregnant according to central/local lab or CRF AE page).
Study Procedures	Excluded Conmeds	N/A	Mixed (monitoring and clinical database)	CRF Prior Diabetes Therapies / Concomitant Therapy panel data to indicate not compliant with entry criteria #43 and study-specific restriction on concomitant therapies Table ITSI.5 in the study protocol. Also identified by CRA as captured in sCTMS.
Study Procedures	Visit Schedule Criteria	N/A	Programmable (clinical database)	CRF data indicate that two consecutive office visits are completely missing.

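### The Safety and CGM Populations are grouped by assigned insulin with no as-received analysis, so events during a dispensing error would be counted under the insulin the patient did not receive

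*SAP*

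**What the plan says.** SAP 6.1, Table ITSI.6.1, admits to the Safety Population "All randomized patients who receive at least 1 dose of the randomly assigned IP". It then fixes the grouping: "Treatment group will be defined on the basis of the treatment the patients are assigned to". The CGM Population carries the same grouping sentence. Protocol 10.2 has the same Safety entry rule but attaches a grouping sentence only to the Randomized population, so the SAP supplied the rule for the other two.

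The primary analysis (SAP 6.11.1) and the treatment-emergent adverse event analyses (Table ITSI.6.2) use the Safety Population. The interstitial glucose reduction rate, a secondary pump-related endpoint, is analysed in the CGM Population.

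The SAP foresees the error. Table ITSI.6.3 includes "Dispensing error: Patient is assigned to a treatment, but site gave a different treatment to the patient", to be identified through monitoring. Important deviations "will be summarized by treatment group for all randomized patients" and are listed in the study report. Neither document plans to re-attribute events or to analyse by insulin received.

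Protocol 7.1.3 provides a safeguard: "Site personnel will confirm that they have located the correct vials by entering a confirmation number found on the vials into the IWRS".

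**The concern.** Set occlusion and infusion site reactions depend on the insulin actually in the set. The two products differ in excipients (Protocol 3.2), and that difference is why the trial exists. If a patient assigned to LY900014 is handed lispro, an occlusion in that time says something about lispro but would be tabulated under LY900014, or the reverse.

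No other rule repairs this. Pump-related analyses "will exclude data (if any) that are collected while patients temporarily are off pump or off IP". However, Protocol Appendix 1 defines investigational product to include a product used as a reference, so time on the wrong blinded vial is not clearly time off IP. Adverse event analyses keep everything collected "during the course of the entire 6-week treatment period for each treatment group regardless of IP use".

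The entry rule has a second effect. A patient given only the wrong insulin, for example one who leaves in Period I, never received the assigned product. That patient's events would leave the Safety Population altogether.

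The direction matters because Protocol 10.1 describes a safety comparability trial with no margin and no powered hypothesis. Attenuation makes the products look more alike.

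**Working it through.** **Inputs.** The plan expects 42 completers, 12% dropout and 48 randomized (Protocol 10.1, SAP 5.2). Each period lasts 6 weeks. Blinded vials are dispensed at Visits 3 and 4 (weeks 0 and 2) and Visits 6 and 7 (weeks 6 and 8) (Protocol Section 2). If vials last until the next dispensing, the first supply in a period covers 2/6 = 1/3 of it and the second 4/6 = 2/3. The documents give no dispensing error rate, so 1, 2 and 4 affected patients are assumed.

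**The plan's own figure.** 42 / (1 − 0.12) = 47.7, rounded up to 48. It reproduces.

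**Dilution.** Let D be the true mean paired difference in rates, N = 42 pairs, m the number of affected patients and f the fraction of one period spent on the wrong insulin. Assume a constant event rate and no period effect. An affected patient then has expected difference (1 − f)D, and the expected mean is D(1 − mf/N). A patient with both periods swapped has −D, and the expected mean is D(1 − 2m/N). The swapped patient is taken to remain in the Safety Population.

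| Error | Loss per patient | m = 1 | m = 2 | m = 4 |
|---|---|---|---|---|
| First supply of a period wrong | (1/3)/42 | 0.8% | 1.6% | 3.2% |
| Second supply of a period wrong | (2/3)/42 | 1.6% | 3.2% | 6.3% |
| Whole period wrong | 1/42 | 2.4% | 4.8% | 9.5% |
| Full sequence swap | 2/42 | 4.8% | 9.5% | 19.0% |

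**Effect on the planned test.** The Wilcoxon signed-rank test does not test the mean, so the effect was also simulated: 2,000 trials per setting, 42 pairs, 2-sided 0.05. The event model is the one removed by amendment (a) and serves only as an illustrative assumption: 0.44 against 2 events/patient/30 days, negative binomial, dispersion 0.29.

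With variance mu + mu²/0.29 and independent periods, power with no error was 80.4%, in line with the removed statement of at least 80%.

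- Full swaps in 1, 2 and 4 patients gave 76.4%, 72.1% and 60.8%.
- Whole-period errors in 1, 2 and 4 patients gave 79.1%, 77.8% and 72.7%.

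The simulation error near 80% is about √(0.8 × 0.2/2000) = 0.9 percentage points. With the other reading of the dispersion parameter, or with a patient effect shared across periods, power at this contrast stayed at 96% or more even with four swaps. The power loss therefore depends heavily on the assumed model.

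**Direction in a single trial.** Across the simulated settings, one swapped patient moved the mean difference toward zero in 31% to 76% of trials and away from zero in 4% to 21%. It was unchanged in the rest.

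**The case against.** The strongest reply is that this may never arise. Vials are assigned by IWRS and confirmed by number, and used vials are returned with drug accountability at Visits 3, 4, 6, 7 and 9. Errors that do occur would be visible in the deviation summary and listing. Grouping by assignment also preserves the randomized contrast, and no stated comparability criterion is crossed by a shift of 1% to 5%. All of this stands, and it keeps the point small. It does not make the attribution right when an error happens, and a listing does not move an event to the other column.

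A reader might infer three stronger things that the documents do not support.

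- **That every dispensing error biases toward no difference.** Attenuation is an average effect and needs a true difference to act on. One error can move the estimate either way. A patient who never received the assigned product is excluded rather than miscredited, and a patient dosed in only one period is outside the primary paired test.
- **That all safety results are affected.** Laboratory data have no by-treatment summary (SAP 6.11.9), and immunogenicity is summarised overall without comparison (SAP 6.11.11.1).
- **That the SAP contradicts the protocol.** Protocol 10.2 does not say how the Safety Population is grouped, so the SAP fills a gap.

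**Conclusion.** The point holds as a modest improvement. The stated rule would attribute events to the wrong insulin if a dispensing error occurred, and no planned analysis would correct it. The expected loss per affected patient among 42 pairs ranges from 0.8% (one early supply wrong) to 4.8% (both periods swapped). The single-supply figures at the low end are the relevant ones for an isolated error at one visit; 4.8% requires wrong supplies throughout both periods. The figures assume a constant event rate, no period effect and a true difference. They are zero without an error, and how likely an error is cannot be judged from the documents. For rare safety events the mean is beside the point: one case under the wrong product is a reporting error in its own right.

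**What to change.** Amend SAP Table ITSI.6.1 and the sections that depend on it, before unblinding:

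1. Define Safety entry as at least one dose of either randomized investigational product.
2. Attribute safety and pump-related events, and the exposure time in the rate denominators, to the insulin actually in use at the time. This settles periods that contain vials of both insulins. Apply the same rule to the interstitial glucose reduction rate in the CGM Population.
3. For the primary signed-rank test, compute each patient's rate per insulin received, and leave out patients who received only one insulin because they have no between-treatment pair.
4. Keep grouping by assignment for the Randomized Population.

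Identify what was received from IWRS vial assignment, drug accountability and monitoring records together. IWRS alone may not be enough, since it holds the assigned and confirmed vial and the SAP expects this error to be found by monitoring. Programming can proceed on the scrambled treatment codes described in SAP Section 7.

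At a minimum, pre-specify this as a sensitivity analysis beside the assigned-treatment analysis, to be run if any dispensing error is found.

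The change needs no new patients or procedures. It costs some programming and vial reconciliation, and possibly the loss of a pair.
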